3. STUDY OBJECTIVES

There remains uncertainty with regards to longer term outcomes among women receiving mesh slings for stress urinary incontinence, and this project seeks to address knowledge gaps for long term outcomes among mesh implantations by leveraging electronic health record data across 5 participating health systems.

Specific Aims: This project seeks to provide a proof of concept for post-market medical device surveillance by assessing the capacity of routinely collected electronic health record data to evaluate the long-term adverse outcomes related to synthetic surgical mesh implantation for stress urinary incontinence.

In pursuit of this goal, this project will:

- 1) Assess data element availability among key covariates and exposures among patients undergoing surgery for stress urinary incontinence,
- 2) If data are available, to assess rates of outcomes of mesh erosion, re-operation for SUI, reoperation for mesh revision or removal, chronic pain either as a new or worsening pain or requiring re-operation and voiding symptoms either as a new symptom or requiring reoperation, each with extended surveillance windows after surgery.
- 3) Specifically, this project will evaluate mid-term (>1 year) and long-term (>2 years) adverse events following synthetic surgical mesh implantation (mid-urethral slings) for female SUI.
- 4) Lastly, if the data quality and volume are sufficient, we will develop a risk prediction model for the risk of the each of the outcomes stated above among patients receiving mesh for SUI.

In summary, this project seeks to better understand the safety of mesh used for stress urinary incontinence by leveraging electronic health record data. The FDA intends on incorporating these data into its growing portfolio of evidence in order to help support regulatory decision making on level of risk

for these procedures and recommendations around use of mesh for this indication. This study has the potential to increase medical knowledge regarding these devices.

4. STUDY DESIGN

This project will be a multi-site retrospective cohort analysis of trans-vaginally placed synthetic midurethral slings (MUS) implanted in patients for the indication of stress urinary incontinence for mid- and long-term outcomes (1 year and greater). We will identify all patients at each of the sites that have received a MUS through administrative and device implantation data. The key exposures will be MUS devices identified by administrative codes. Because ascertainment of the surgical approach is critical to the evaluation of post-operative complications, and has differing rates depending on the approach, we will determine which approach was used: Retropubic MUS (RPMUS), Transobturator MUS (TOMUS), Single-Incision Sling (SIMUS), or Adjustable Sling (AMUS). In prior work at Mayo, determination of the surgical approach was present in 100% of cases in the operative notes. We will also identify all patients that received a surgery for SUI without mesh (autologous or cadaveric fascial sling or burch colposuspension or bulking agents) and evaluate the same outcomes of interest in that population separately to provide an indirect comparison group. No direct comparison of mesh and non-mesh groups will be conducted. Patients with concomitant surgeries at the time of trans-vaginal mesh implantation for SUI will be included. The primary outcomes of interest are long-term safety outcomes relevant to these devices and defined in Section 7. In addition, using the Mayo Clinic data, we will be able to validate the electronic data with the manually curated data from 2010-2012². We will leverage this data to better understand how much of the data can be electronically generated and where additional information would need to be collected in an electronic environment.

Beyond the variables collected for exposures, outcomes, and cohort inclusion/exclusion, important covariates relevant to the device exposures and outcomes, and present prior to the surgery, will also be collected.

These include:

- Patient demographics
- Chronic pain
- Prior abdominal surgery
- Receipt of urodynamic testing (structured data will not have the results)
- BMI
- Insurance payer
- Chronic clinical conditions will be aggregated using the Healthcare Cost and Utilization Project's Clinical Classification Software, which reduces all ICD-9/10 codes to 285 clinically meaningful groups⁴². The CCS has been updated to include ICD-10, which is important, as this project will span ICD-9 and 10 eras.
- Medication exposures will be aggregated using the PCORNet⁴³ instantiation of the RxNorm controlled vocabulary⁴⁴ and leveraging this vocabulary to the Anatomical Therapeutic Chemical (ATC) Level 4 groupings, which are clinically relevant drug classes.

Some co-variates may not be ascertainable in some participating sites' PCORNet CDM instances, and this will be explored and reported. Each of the outcomes, exposures, and covariates will be analyzed for counts in each site and a summarization and report will be provided to characterize the data at each site. Stratified reporting of those receiving surgery for SUI with mesh and those without mesh will be performed.

Next, if the characterization of the data is sufficient for the task, we will pursue a Cox proportional hazards model analysis, with each of the outcomes assessed from the time of the surgery as a time-to-event. We will censor the time-to-event analysis with death or loss to follow-up, defined as a time period

Version 2.0

[15 July 2020]

>2 years from last applicable encounter of primary care, Obstetrics & Gynecology, or Urology. The models will be executed at each institutional separately using LASSO Cox to determine the consistently included covariates in each institution⁴⁵. We will then use the final variable list and utilize the method described by Lu and colleagues that uses a distributed analysis approach to obtain an exact model solution without sharing case level data (only intermediate and aggregate model coefficients and matrices)⁴⁶.

Because bootstrapping combined with the distributed analysis method would be computationally intensive, we will utilize 10-fold cross validation across all sites for internal validation of the risk model. We assessed overall discrimination using Harrell's concordance statistic (C-statistic)⁴⁷. To provide calibration assessments, we will also evaluate the model at fixed time points of 1 year and 2 year for each outcome using the AUC and the Estimated Calibration Index (ECI)⁴⁸. The ECI looks at the squared difference between the predicted probability and an estimated observed probability, ranging between 0 and 100, with 0 meaning perfect calibration. Additionally, we will graphically analyze calibration by investigating the smoothed observed-to-predicted probability plot⁴⁸.

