defined as requiring at least one outpatient medicine specialty or relevant
(Obstetrics & Gynecology, Urology) sub-specialty encounter in the 12
months prior to implantation. For this sensitivity analysis, we will also
exclude patients with prior pelvic organ prolapse or stress urinary
incontinence surgeries. As an additional comparator population, we will

Synthetic Mid-Urethral Slings for Stress Urinary Incontinence in Women	
Protocol 1	

	identify all those who underwent a procedure for SUI but did not receive mesh implantation.
Description of Sites/Facilities:	The Participating Sites for this Study include Vanderbilt University Medical Center, Lahey Hospital & Medical Center, Mayo Clinic, Weill-Cornell, and Yale New Haven Health System. In addition, as a data quality validation check, we will have access to a manually collected and curated 3,472 patient case series at Mayo Clinic from 2002 to 2012 of patients that underwent surgery for incontinence ² . For the routine EHR data sources, the valid dates will be from 2010 to the most recently available data.
	As a preliminary assessment of data volume, each site queried their data for CPT 57288 sling operation for stress incontinence. VUMC had a total of 6,106 from 2010-2018, and an average of ~500 cases a year for the last 4 years. Mayo Clinic had a total of 5,413 cases from 2010-2018, and an average of ~500 cases a year for the last 4 years. Weill-Cornell had 887 cases from 2010 to 2019, and an average of 150 procedures a year over the last 4 years. Yale New Haven Healthcare System has data from 2013-2018, and about 170 procedures in the most recent 6-month period. Lahey Clinic had 108 surgeries in 2018, and an average of 84 procedures a year over the last 4 years.
Description of Study Intervention:	This is an observational study design, and there are no direct interventions for patients, thus a Data and Safety Monitoring Plan is not required, and a Data and Safety Monitoring Board is not required.
Study Duration:	1 year, Start Date 02/17/2020, End Date 03/15/2021.
Duration of Data Captured:	2010-2019 in EHR Data

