6. STUDY PROCEDURES

We will access the routinely collected observational data from electronic health records at Vanderbilt University Medical Center, Lahey Hospital & Medical Center, Mayo Clinic, Weill-Cornell, and Yale New Haven Health System for this study. For the routine EHR data sources, the valid dates will be from 2010 to the most recently available data. There are no patient recruitment or retention barriers in this project as all data are observational cohort data. There are significant issues around data ascertainment bias that will be addressed in more detail in Study Design & Methods. Patient level data will not leave each institution, only aggregate data or distributed regression analyses, which will remove the requirement for a data sharing agreement and streamline the execution of the project. We will leverage each site's PCORNet common data model and the VUMC site will build the code to transform the data from the PCORNet common data model to the flat analytic file necessary for statistical work.

This project will be a multi-site retrospective cohort analysis of trans-vaginally placed synthetic midurethral slings (MUS) implanted in patients for the indication of stress urinary incontinence for mid- and long-term outcomes (1 year and greater). The key exposures will be MUS devices identified by administrative codes and identifying all patients at each of the sites through administrative and device implantation data. Surgical approaches (Retropubic MUS, Transobturator MUS, Single-Incision Sling, and Adjustable Sling) will be determined through natural language processing of operative notes. We will also identify all patients that received a surgery for SUI without mesh (autologous fascial sling or burch colposuspension). The primary outcomes of interest are long-term safety outcomes relevant to these devices and defined in Section 7. In addition, using the Mayo Clinic data, we will be able to validate the

Version 2.0 [15 July 2020]

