7. STUDY OUTCOMES

The primary outcomes of interest are:

- Re-operation (revision, incision, excision, removal) or mesh removal
- Chronic pain, defined as pain persisting at least three months after surgery⁴⁹
- Voiding symptoms, defined as recurrence of incontinence or new retention.

All outcomes are determined in the surveillance period after surgery. Re-operation or mesh removal is defined as a surgery for any kind of mid-urethral sling, urethral bulking agent, bladder neck pubovaginal sling (autologous or allograft), or revision for mesh exposure. Resumption of voiding symptoms was defined as subsequent urinary retention, urinary incontinence, and sling revision for urinary retention. Chronic pain is defined as a new post-operative pain score >3 of 10 on vital sign data occurring over at least 3 months or greater of duration, or diagnosis codes related to abdominal and pelvic pain.

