		 Mesh exposure and erosion (ICD9/10 629.31, 629.32/T83.711, T83.721) Urinary Retention (CPT Code 53500, ICD 9/10 788.20, 788.21/R33.0, R33.8-R33.9) Urgency of urination (ICD9/10 788.63/R39.15) Urge incontinence (ICD9/10 788.31/N39.41) Bowel injury (ICD9/10 569.83/S36) Bladder/urethral injury (ICD9/10 596.6,867.0/S37) Infection (ICD9/10 686.9,998.5,999.3,998.51,998.59/T81) Retropubic hematoma (ICD 9/10 568.81,,568.81,459.0/K66.1) Retopubic hematoma (ICD 9/10 568.81,,568.81,459.0/K66.1) Retopubic hematoma (ICD 9/10 568.81,568.81,459.0/K66.1) Bulking Injection CPT 51715, ICD 9/10 59.72/ PCS 3E0K3GC Laparoscopic Retropubic Urethropexy CPT 51990, 51992, 51999 Abdominal Retropubic Urethropexy CPT 51840,51841 Needle Bladder Neck Suspension CPT 51845 Kelly plication CPT 57220 Cystourethroplasty CPT 51800 Subtypes: Stress incontinence, female/mixed incontinence (ICD9/10 625.6,788.33/N39.46) Stress incontinence (female) (male)(ICD10 CM N39.3) 		
Outcome	Mesh Removal	 General, CPT 57287-Removal or revision of sling for stress incontinence (fascia or synthetic) ***some erosions managed surgically may have been coded by a different CPT (i.e. 57295 revise vaginal graft via vaginal approach) and not CPT 57287, which indicates a sling revision/removal. 	Yes	Possible Options: (a surgery for any kind of mid-urethral sling, urethral bulking agent, black neck pubovaginal sling (autologous or allograft), or revision for mesh exposure). Represented as a Date, allows time-to-event analysis.
Outcome	Post-Procedural Pain	?, mix of vital sign (pain score >3 of 10 on vital sign data) and likely free text. Also, diagnosis codes related to abd/pelvic pain (if prior pain free).	Some portion	Would have to exclude prior chronic pain or detect specific mention of new pain (free text). Could analyze group with no pre-surgical pain,

Protocol 1				[15 July 2020]
				otherwise probably beyond scope. Date/Time of first post- op occurrence.

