		N39.498 Other specified urinary incontinence		
		Prolapse		
		ICD 9:		
		618.01 Cystocele, midline		
		618.02 Cystocele, lateral		
		618.03 Urethrocele		
		618.81 Incompetence or weakening of		
		pubocervical fascia		
		618.1 Uterine prolapse without mention of		
		vaginal wall prolapse		
		618.2 Uterovaginal prolapse, incomplete		
		618.3 Uterovaginal prolapse, complete		
		618.4 Uterovaginal prolapse, unspecified		
		618.5 Prolapse of vaginal vault after		
		hysterectomy		
		618.6 Vaginal enterocele, congenital or acquired		
		618.84 Cervical stump prolapse		
		618.04 Rectocele		
		618.05 Perineocele		
		618.82 Incompetence or weakening of		
		rectovaginal fascia		
		618.00 Unspecified prolapse of vaginal walls		
		618.09 Other prolapse of the vaginal walls		
		without mention of uterine prolapse		
		618.7 Old laceration of muscles of pelvic floor		
		618.83 Pelvic muscle wasting		
		618.89 Other specified genital prolapse		
		618.9 Unspecified genital prolapse		
		ICD-10 CM :		
		N81.0 Urethrocele		
		N81.10 Cystocele, unspecified		
		N81.11 Cystocele, midline		
		N81.12 Cystocele, lateral		
		N81.2 Incomplete uterovaginal prolapse		
		N81.3 Complete uterovaginal prolapse		
		N81.4 Uterovaginal prolapse, unspecified		
		N81.5 Vaginal enterocele		
		N81.5 Vaginal enterocele		
		N81.89 Other female genital prolapse		
		N99.3 Prolapse of vaginal vault after		
	1	1953.5 I TOTAPSE OF VAGITAL VAULT ALLEL	1	1
		hysterectomy		
		hysterectomy		
Exposure	SUI with Mesh	Admin Codes CPT 57288	Yes	Capture as date/time

Version 2.0 [15 July 2020]

Protocol 1				[15 July 2020]
Exposure	SUI without Mesh	Admin Codes	Yes	Capture as date/time
	IVIES11	CPT/ICD-9-CM/ICD-10-PCS 51715/ 59.72/3E0K3GC, 3E0K4GC Injection of implant into the urethra and/or bladder neck (collagen implant)		
		CPT/ICD-9-CM/ICD-10-PCS 51990, 51992/59.5/OTSD0ZZ, OTSD4ZZ Laparoscopic urethral suspension, laproscopic sling procedure		
		CPT/ ICD-9-CM/ICD-10-PCS 51841, 51840/ 59.5/0TSD0ZZ, 0TSD4ZZ Anterior vesicourethropexy, or urethropexy (eg, Marshall- Marchetti-Krantz, Burch)		
		CPT/ICD-9-CM/ICD-10-PCS 51845/59.5/0TSD0ZZ, 0TSD4ZZ Abdominovaginal vesical neck suspension		
		CPT /ICD-9-CM/ICD-10-PCS 57220/ 59.3/0TSC0ZZ, 0TSC4ZZ Kelly plication of urethrovesical		

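### The non-mesh comparator is listed differently in Sections 4, 6 and the appendix, and where bulking agents are included a second injection counts as a re-operation, so the non-mesh rate depends on the section followed

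*Protocol*

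**What the plan says.** The comparator is described in four places in the protocol:

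- **Synopsis, Target Population** is generic: it will "identify all those who underwent a procedure for SUI but did not receive mesh implantation".
- **Section 4** names the procedures: "autologous or cadaveric fascial sling or burch colposuspension or bulking agents".
- **Section 6**, in an otherwise similar paragraph, names "autologous fascial sling or burch colposuspension". Cadaveric slings and bulking agents are absent.
- **Section 13, appendix row for SUI without mesh**, gives codes. It includes "Injection of implant into the urethra and/or bladder neck (collagen implant" (CPT 51715), laparoscopic suspension and laparoscopic sling (51990, 51992), Burch-type urethropexy (51840, 51841), "Abdominovaginal vesical neck suspension" (51845) and Kelly plication (57220). The general sling code stands in the row for SUI with mesh: "Admin Codes CPT 57288".

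On the outcome side, Section 7 states: "Re-operation or mesh removal is defined as a surgery for any kind of mid-urethral sling, urethral bulking agent", among other procedures. The appendix re-operation list contains "Bulking Injection CPT 51715". Section 4 applies the mesh group's outcomes to the non-mesh group as well, and Section 9.1 intends the two to be read side by side without a formal test.

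**The concern.** Two things interact. First, membership of the comparator changes with the section followed. Second, where bulking is included, one code both admits a woman to the cohort and counts as her event. The protocol gives no minimum interval and no rule for a repeat injection.

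Re-operation is a primary outcome, and the non-mesh column exists so that readers can set it beside mesh. The synopsis reports mesh by surgical approach but treats SUI surgery without mesh as one stratum. A mixture of injections and surgical procedures would therefore not be visible in the table. Patient-level data stay at the sites, so a cohort definition settled late means rerunning the extraction at every site.

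**Working it through.** The plan states no comparator rate, so there is no figure to reproduce. The check is a comparison of the lists, followed by an illustration.

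**Step 1: the three specific lists.**

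| Procedure | Section 4 | Section 6 | Appendix row |
|---|---|---|---|
| Autologous fascial sling | yes | yes | not seen |
| Cadaveric fascial sling | yes | no | not seen |
| Burch | yes | yes | yes |
| Bulking agent | yes | no | yes (51715) |
| Laparoscopic sling, abdominovaginal suspension, Kelly plication | no | no | yes |

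Burch is the only procedure found in all three. The appendix row breaks off mid-phrase at Kelly plication in the text available, so the two entries marked not seen may have been lost when the table was read.

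**Step 2: follow one woman.** Her first SUI procedure is a bulking injection and she later has a second.

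- Under Section 4 or the appendix, the first injection is her index procedure and the second meets the re-operation definition.
- Under Section 6, she is not in the comparator.
- The Section 5 exclusion for earlier SUI surgery does not change this, because it looks back from the index procedure.

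**Step 3: illustration of size.** Let s be the bulking share of the comparator, rb the repeat-injection rate and r0 the re-operation rate of the other non-mesh procedures. A plain mixture gives

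pooled rate = (1 − s) × r0 + s × rb.

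Both s and rb are assumptions: s is 10–30% and rb is 10–40%. For r0, Section 1.1 quotes 5.5% at 5 years from a mesh-sling cohort and 14.5% after a median of 9 years from a US claims database. Neither is offered as a non-mesh rate for this study.

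- r0 = 5.5%, s = 10%, rb = 10%: 0.9 × 5.5 + 0.1 × 10 = 5.95%
- r0 = 5.5%, s = 10%, rb = 40%: 0.9 × 5.5 + 0.1 × 40 = 8.95%
- r0 = 5.5%, s = 30%, rb = 10%: 0.7 × 5.5 + 0.3 × 10 = 6.85%
- r0 = 5.5%, s = 30%, rb = 40%: 0.7 × 5.5 + 0.3 × 40 = 15.85%
- r0 = 14.5%, s = 30%, rb = 10%: 0.7 × 14.5 + 0.3 × 10 = 13.15%, below the base
- r0 = 14.5%, s = 30%, rb = 40%: 0.7 × 14.5 + 0.3 × 40 = 22.15%

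Under Section 6, s = 0 and the rate is r0. The pooled rate rises only when rb exceeds r0.

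**The case against.** **The consequence is limited.** The protocol rules out a direct comparison, its stated aim is proof of concept, and aim 4 restricts the risk model to mesh recipients. Mesh erosion and mesh revision or removal are untouched. All of this stands, and it confines the point to a descriptive rate.

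**The lists differ less than they seem to.** On bulking, Section 4 and the appendix agree and the synopsis is compatible with both; only Section 6 is shorter. That is fair, but Section 6 is current text and nothing says which passage governs. The synopsis refers to the appendix codes for mesh exposure only.

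Three stronger readings are tempting, and the document does not support them:

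- *Fascial slings have no code in the plan, or would be classed as mesh.* The broken row is weak evidence of absence. A separate appendix list drawn from a cited study gives ICD-9 59.79 for pubovaginal sling.
- *The non-mesh rate is inflated by a known multiple.* One could add the repeat-injection risk to the full 5.5% base: (1 − s) × 5.5% + s × [1 − 0.945 × (1 − rb)]. That gives 6.4% (1.17-fold) at s = 10%, rb = 10% and 16.8% (3.1-fold) at s = 30%, rb = 40%. This form can only rise, and its upper end depends on choosing the low base.
- *Mesh will look better for a purely definitional reason.* The protocol does not say whether a second injection is part of a planned course or a treatment failure. If it is a failure, counting it is legitimate. Section 7 also counts bulking after mesh.

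The code overlap is not unique to bulking either: the other non-mesh codes in the appendix row also appear in the re-operation list. What sets bulking apart here is that Section 6 removes it from the cohort, and that the meaning of a repeat injection is left open.

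**Conclusion.** The point holds as a contradiction in the cohort definition combined with an overlap between index procedure and outcome. The non-mesh rate of a primary outcome depends on which section is followed. Where bulking is included, that rate mixes repeat injection with re-operation after surgical procedures.

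Neither size nor direction can be derived from the document. The range of about 6.0% to 15.9% rests on an assumed bulking share, an assumed repeat rate and a borrowed 5.5% base. At a 14.5% base the pooled rate can move either way. The plan should be corrected, but the error reaches only the side-by-side description and leaves the mesh-only risk model unaffected.

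**What to change.** 1. Put one comparator list, chosen by the sponsor and investigators, into Sections 4 and 6 and the appendix code row, and check that every named procedure has its code there.
2. Report index bulking procedures as their own stratum, separate from surgical non-mesh procedures.
3. State how a repeat 51715 after index bulking is counted, and show the non-mesh re-operation rate both with and without it. Simply dropping repeat injections from the non-mesh rate, while bulking after mesh still counts, would apply different outcome rules to the two columns.

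The cost is protocol wording, one extra stratum and one extra reporting line. Non-mesh strata become smaller and their rates less precise. No new data are needed: 51715 is already in both code lists and is captured with its date.

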Next, if the characterization of the data is sufficient for the task, we will pursue a Cox proportional hazards model analysis, with each of the outcomes assessed from the time of the surgery as a time-to-event. We will censor the time-to-event analysis with death or loss to follow-up, defined as a time period >2 years from last applicable encounter of primary care, Obstetrics & Gynecology, or Urology. The models will first be developed at each institutional separately using LASSO Cox to predict time to event for each of the outcomes of interest. We will use the variables retained in any of the individual site models, and develop a Cox model using the method described by Lu and colleagues (WebDISCO) that uses a distributed analysis approach to obtain an exact model solution without sharing case level data (only intermediate and aggregate model coefficients and matrices)¹. This method is being used to protect patient data by processing it at the local institutions and only sharing intermediate modeling statistics (aggregates) between sites.

Because bootstrapping combined with the distributed analysis method would be computationally intensive, we will utilize 10-fold cross validation across all sites for internal validation of the risk model. We assessed overall discrimination using Harrell's concordance statistic (C-statistic). To provide calibration assessments, we will also evaluate the model at fixed time points of 1 year and 2 year for each outcome using the AUC and the Estimated Calibration Index (ECI). The ECI looks at the squared difference between the predicted probability and an estimated observed probability, ranging between 0 and 100, with 0 meaning perfect calibration. Additionally, we will graphically analyze calibration by investigating the smoothed observed-to-predicted probability plot.

Target Population:All women aged 18 or greater undergoing transvaginal surgery for stress
urinary incontinence with or without mid-urethral mesh sling implantation
are eligible for inclusion in the EHR data. Determination of the appropriate
mesh exposure during surgery will be determined through administrative
CPT procedure codes, as defined in the appendix. No exclusions will be
applied based on race or ethnicity. As a separate sensitivity analysis to
reduce potential lack of outcome ascertainment, we will exclude all
patients that do not also have continuity of care within the data site,

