9. STATISTICAL ANALYSIS PLAN (SAP)

9.1 STATISTICAL METHODS

Each of the outcomes, exposures, and covariates will be analyzed for counts at each site and a summarization and report will be provided to characterize the data. Stratified reporting of those receiving surgery for SUI with mesh and those without mesh will be performed. While this will allow for indirect comparison of these sub-populations side by side, no direct statistical comparisons between the groups will be made.

Next, if the characterization of the data is sufficient for the task, we will pursue a Cox proportional hazards model analysis, with each of the outcomes assessed from the time of the surgery as a time-to-event. We will censor the time-to-event analysis with death or loss to follow-up, defined as a time period >2 years from last applicable encounter of primary care, Obstetrics & Gynecology, or Urology. The models will be executed at each institutional separately using LASSO Cox to determine the consistently included covariates in each institution²⁵. We will then use the final variable list and utilize the method described by Lu and colleagues that uses a distributed analysis approach to obtain an exact model solution without sharing case level data (only intermediate and aggregate model coefficients and matrices)⁴⁶.

Because bootstrapping combined with the distributed analysis method would be computationally intensive, we will utilize 10-fold cross validation across all sites for internal validation of the risk model. We will assess overall discrimination using Harrell's concordance statistic (C-statistic)⁴⁷. To provide calibration assessments, we will also evaluate the model at fixed time points of 1 year and 2 year for each outcome using the AUC and the Estimated Calibration Index (ECI)⁴⁸. The ECI looks at the squared difference between the predicted probability and an estimated observed probability, ranging between 0 and 100, with 0 meaning perfect calibration. Additionally, we will graphically analyze calibration by investigating the smoothed observed-to-predicted probability plot⁴⁸.

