11. RESULTS DISSEMINATION

No case level or individual patient level information will be shared between sites or publicly. All other artifacts of the research study will be shared. This includes study design, data cleaning and transformation code, statistical analysis code, covariate definitions, aggregate data summaries, and final prediction models for each outcome. We will first disseminate the results to the FDA and NEST, and then will follow their guidance for when the materials should be submitted for publication. Should any concerns arise from FDA requiring the information to be released prior to publication for safety reasons, we will involve all sites, the FDA, and NEST in these discussions.

At present, we do not anticipate that we will have device specific information available within the electronic health record data that would allow us to issue specific device safety information, but instead plan on a general analysis by surgical approach and implant type.

Use of Evidence: The FDA has been an important collaborator in the development of this project, as represented by [name], Deputy Director of Clinical Affairs and Chief Medical Office of the FDA

Center for Devices and Radiological Health. As the sponsor of this project, he has provided critical guidance on the particular outcomes, device exposures, and surgical procedures and indications that are of interest to the FDA. There has been an explicit discussion that the evidence generated by this project could impact FDA decision making around the use of synthetic surgical mesh implanted through a transvaginal approach for the indication of stress urinary incontinence, and that there is a relative lack of mid and long-term outcome data in these devices for this indication. [name] will be an active participant in the research protocol throughout the project and will diffuse the findings to the relevant FDA personnel that would need access to the results. This project does not have any current projected impact on coverage other than through possible indirect effect on future FDA decisions.

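### The risk models are validated only across all sites together, with no performance by site or at a held-out site, so failure at a smaller site could go unseen

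*Protocol*

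**What the plan says.** The validation text is nearly the same in the Synopsis (Statistical Methods) and Sections 4, 6 and 9.1. Section 4 states "we will utilize 10-fold cross validation across all sites for internal validation of the risk model. We assessed overall discrimination using" Harrell's C-statistic. Section 9.1 puts the last part in the future tense: "We will assess overall discrimination using" the same statistic. AUC, the Estimated Calibration Index (ECI) and a smoothed plot of observed against predicted risk follow at one and two years for each outcome.

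The data rule is stated several times. The Synopsis describes the distributed Cox method as "only sharing intermediate modeling statistics (aggregates) between sites". Section 11 says "No case level or individual patient level information will be shared between sites or publicly". Section 6 lets aggregates and distributed regression results leave a site. Section 10.2 foresees returning aggregated data to the sites so that all-site summaries can be calculated.

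On differences between sites, Section 4 warns "Some co-variates may not be ascertainable in some participating" sites. Section 8.1 says that Lahey alone uses OMOP rather than PCORNet and alone has not had the extensive data quality assessment. The Date of Death row of the appendix table says that Lahey records deaths only within the institution. The reporting planned by site covers counts of outcomes, exposures and covariates. Model performance is not part of it.

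**The concern.** A multi-site model can look sound overall and still fail at one hospital, because a covariate is missing there, outcomes are captured differently or follow-up ends differently. The Protocol names causes of this kind but fixes a validation that would not show the result. Folds drawn across all sites most naturally contain women from every site, so no site is ever scored by a model that it did not help fit.

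The aim is a proof of concept for device surveillance from routine records, and Section 11 lists the final prediction models among the materials to be shared. Whether a model carries over to another health system is therefore a question that readers will ask. The five sites could answer part of it, and the plan does not use them for that.

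A second, smaller point is what the overall C means. Harrell's C is the share of concordant pairs among comparable pairs. If all women are pooled, most pairs join women from different sites, and these cannot be scored directly without case-level data. If only pairs within a site are used, it is a different quantity. The Protocol does not say which applies.

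**Working it through.** The Protocol states no target for C and no sample size for this step, so there is no figure of its own to reproduce.

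**Inputs.** The Synopsis (Description of Sites/Facilities) gives preliminary counts of sling operations: Vanderbilt 6,106, Mayo 5,413, Weill-Cornell 887. It gives no totals for Yale or Lahey, so these are assumed:
- Yale: 170 (the latest half-year alone) to 170 × 12 half-years = 2,040.
- Lahey: 108 (2018 alone) to 84 × 9 years = 756.

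**Share of women at the two large sites.** 6,106 + 5,413 = 11,519.
- High assumption: 11,519 / 15,202 = 0.758.
- Low assumption: 11,519 / 12,684 = 0.908.

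**Share of pairs that cross sites**, 1 − Σn²/N², taking similar event rates at all sites:
- High: 1 − 72,103,710 / 231,100,804 = 0.688.
- Low: 1 − 67,411,138 / 160,883,856 = 0.581.

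**Weight of each site in a pair-weighted within-site C.** Vanderbilt and Mayo together have 66,583,805 / 72,103,710 = 0.923 (high) or 66,583,805 / 67,411,138 = 0.988 (low). At the high assumption Yale has 0.0577, Weill-Cornell 0.0109 and Lahey 0.0079. If C at one site fell from 0.70 to 0.50, the combined value would drop by 0.20 times that weight: 0.0115 for Yale, 0.0022 for Weill-Cornell, 0.0016 for Lahey.

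**Simulation.** Five sites at the high assumption, one risk score, log hazard ratio 0.7 per SD, exponential event times, uniform censoring from 0.5 to 9 years, about 1,000 events. Each line is a single draw, so small differences are partly noise.

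| Scenario | Pooled C | Within-site C | C at affected site |
|---|---|---|---|
| No failure, draw 1 | 0.7003 | 0.7046 | – |
| No failure, draw 2 | 0.6972 | 0.6940 | – |
| No failure, event rates differ by site | 0.6866 | 0.6851 | – |
| No discrimination, Weill-Cornell size | 0.6897 | 0.6915 | 0.578 |
| No discrimination, Lahey size | 0.6811 | 0.6884 | 0.457 |
| No discrimination, Yale size | 0.6757 | 0.6887 | 0.526 |
| Score reversed, Lahey size | 0.6711 | 0.6855 | 0.296 |

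The pooled C with a failing Weill-Cornell-size site (0.6897) is higher than in a draw where every site was sound but event rates differed (0.6866). The overall figure alone does not tell these situations apart.

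**Can a pooled C be had from aggregates?** Each site can supply counts by score bin, time bin and event status, and such tables add across sites. With 50 score bins and 30-day intervals the rebuilt C was 0.7002 against an exact 0.7003, and 0.6970 against 0.6972. With 10 bins and 90 days it was 0.6968 and 0.6936, so within 0.0036.

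**The case against.** A reader might infer that the data rule makes the overall C impossible to compute. The documents do not support that. They bar case-level data, while Sections 6 and 10.2 allow aggregates to be exchanged, and the count tables above come close to the exact value. A within-site C needs no cross-site pairs at all. The word *overall* may also mean only over the whole of follow-up, in contrast to the fixed one- and two-year points. On that reading the cross-site share shows no error, only an undefined term.

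A reader might also infer that calibration is bound to look good because every site feeds both training and test data. The Protocol plans no calibration-in-the-large, does not call the folds random, and no calculation supports the inference.

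It can further be said that ten-fold cross-validation is a standard choice for what the Protocol labels internal validation, that modelling depends on the data characterisation being adequate, and that computing details may sit in an analysis plan not shown. All of this is fair. Site-level counts, site-level LASSO fits and chart review of 50 to 100 cases per site will also reveal some differences. But these examine data and variable selection, not how well the common model predicts at each site. The across-site scheme is fixed in the Protocol itself, four times, so the point does not rest on an omission alone.

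**Conclusion.** The concern holds as a gap in the validation design. As written, failure at Weill-Cornell, Yale or Lahey could pass unnoticed, and nothing would show performance at a site outside the fit. In the simulated cases the pooled C was between 0.671 and 0.690 while C at the affected site was between 0.296 and 0.578.

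The sizes rest on assumed Yale and Lahey totals, on preliminary procedure counts taken before the Section 5 exclusions, and on invented effect sizes in single draws. The direction does not: two sites dominate at every volume considered. The lack of a definition for the overall C is a lesser matter of clarity. This is an inexpensive improvement and does not show that the planned analysis is invalid.

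**What to change.** In the Synopsis and Sections 4, 6 and 9.1:

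1. Have each site compute C, the one- and two-year AUC and calibration locally from the common coefficients, and report all five site values.
2. Define the overall C as a weighted average of within-site values, or as a pooled value built from aggregate counts. Because a pair-weighted average is still dominated by two sites, always show it with the site values. Build any all-site calibration plot from counts in fixed predicted-risk bins.
3. Add leave-one-site-out validation: select variables and fit on four sites, then score at the fifth. Report C, calibration slope and observed/expected for each held-out site. The held-out site's LASSO result must be left out of variable selection. Ten-fold results can stay as secondary.

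The cost is wording, code and up to five additional distributed fits per outcome if ten-fold is kept. If sites replace the folds, it is five fits instead of ten. Estimates at the smallest sites will be imprecise: with about 50 events, a sound Lahey-size site gave C of 0.692 in one draw and 0.776 in another, so intervals are needed. Fine count tables may have small cells that need disclosure control, which limits bin width.
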